## 4 SAMPLE SIZE

This study is designed to evaluate time to prostate cancer progression (pathological or therapeutic progression) as the primary endpoint. The overall two-sided type I error for this study is set at 0.05 level. The characteristics of time to prostate cancer progression (pathological or therapeutic progression) are used to determine the total sample size and overall duration.

A sample size of 222 subjects randomized in a 1 to 1 manner accrued over one year, a study duration of 3 years, loss-to follow-up of 16%, an assumed underlying hazard ratio of 0.52 and a three year median time-to-progression for the Control group (0.2310 rate) will result in 72 events (Fleshner et al., 2012). This sample size is sufficient to power this study at 80% with a two-sided type I error rate of 5%.

The assumed hazard ratio of 0.52 is consistent with Fleshner et al. (2012). Specifically, the Fleshner study is powered to detect a 39% failure rate reduction in the treated group with respect to a three year 45% failure rate in the control group. We used a more conservative 30% failure rate reduction for the treated group and a 50% three year failure rate for the control group. This resulted in parameter estimates of 0.2310 for the Control group and 0.1189 for the Treatment group, and thus, resulted in the hazard rate of 0.52.

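### The sample-size section says it assumes a 30% reduction in failure rate, but the rate it uses (0.1189) is a 30% failure rate; a 30% reduction gives HR 0.62 and about 52–55% power, not 80%

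*SAP*

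**What the plan says.** Everything is in SAP Section 4 (Sample Size).

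- Design: "A sample size of 222 subjects randomized in a 1 to 1 manner accrued over one year, a study duration of 3 years".
- Further inputs: the effect is "an assumed underlying hazard ratio of 0.52", the control median is three years, and attrition is put at 16% with no period given. These are said to give 72 events.
- Error rate and power: "The overall two-sided type I error for this study is set at 0.05 level", and the section concludes "This sample size is sufficient to power this study at 80% with a two-sided type I error rate of 5" per cent.
- Precedent: the cited placebo-controlled dutasteride trial is described as "powered to detect a 39% failure rate reduction in the treated group with respect to a three year 45% failure rate in the control group".
- This trial's assumption: "We used a more conservative 30% failure rate reduction for the treated group and a 50% three year failure rate for the control group".
- Result attributed to that assumption: "parameter estimates of 0.2310 for the Control group and 0.1189 for the Treatment group", and from these the 0.52.

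**The concern.** The text presents the treatment rate as the consequence of a 30% reduction from a 50% failure rate. It also presents that reduction as more cautious than the cited trial's 39%. The printed rate does not follow from the printed assumption, and the effect actually used is not the more cautious one.

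This paragraph is the only justification of the effect size in the document. A reader facing a null or borderline result would take from it that the trial had 80% power for an effect smaller than the precedent's, and might conclude that a 30% reduction had been reasonably excluded. In fact the 80% belongs to an effect slightly larger than the precedent's, and the effect named in the text would be detected only about half the time.

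**Working it through.** **Inputs, all from SAP Section 4.** 222 subjects, 1:1, accrued over 1 year, 3 years in total; two-sided alpha 0.05; loss 16%; three-year control failure 50%; rates 0.2310 and 0.1189; 72 events; 80% power. Assumption added here: the loss is exponential and reaches 16% at three years, so the loss rate is η = −ln(0.84)/3 = 0.0581 per year.

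**Formulas.**
- Exponential rate from a three-year failure proportion F: λ = −ln(1 − F)/3.
- Event probability for a subject followed for f years: λ/(λ+η) × [1 − exp(−(λ+η)f)], averaged over f uniform from 2 to 3 years.
- Schoenfeld power with d events: Φ(√d/2 × |ln HR| − 1.96).
- Schoenfeld events for 80% power: 4(1.96 + 0.8416)²/(ln HR)².

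**Step 1: reproduce the plan.** HR = 0.1189/0.2310 = 0.5147. Expected events are 45.5 (control) + 26.6 (treated) = 72.1. Power at 72 events is Φ(4.243 × 0.664 − 1.96) = Φ(0.858), about 80.4%. Events required: 72. At the rounded HR of 0.52, power is 79.2%. The 72 events and 80% therefore come from 0.1189.

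**Step 2: find what assumption gives 0.1189.**

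| Reading | Treated failure at 3 years | Rate | HR |
|---|---|---|---|
| 30% relative reduction | 50% × 0.70 = 35% | −ln(0.65)/3 = 0.1436 | 0.621 |
| 30-point absolute reduction | 20% | −ln(0.80)/3 = 0.0744 | 0.322 |
| 30% cut in the hazard | – | 0.70 × 0.2310 = 0.1617 | 0.70 |
| Failure rate of 30% | 30% | −ln(0.70)/3 = 0.1189 | 0.515 |

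Only the last row matches. It is a relative reduction of 1 − 30/50 = 40%.

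**Step 3: compare with the cited trial, using the figures Section 4 prints.** Its 39% reduction must be relative: an absolute cut would leave 6% failing and HR ln(0.94)/ln(0.55) ≈ 0.10, which could not be consistent with 0.52. The relative reading gives 45% × 0.61 = 27.45% and HR = ln(0.7255)/ln(0.55) = 0.537. The effect used here is larger on both scales: 40% against 39%, and HR 0.515 against 0.537. Power at HR 0.537 with 72 events is 75.1%.

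**Step 4: power for the assumption as written (HR 0.621).**
- At 72 events: Φ(4.243 × 0.4756 − 1.96) = Φ(0.058) = 52.3%.
- Events the design would then yield: 45.5 + 31.2 = 76.7, giving 54.9%.
- For 80%: 139 events, or 139/(76.7/222) ≈ 402 subjects under the same accrual, duration and loss.

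**Step 5: sensitivity.** Freedman's formula gives 50.8% at 72 events and 53.3% at 76.7; Lachin–Foulkes gives 53.7% for the 222-subject design. Other readings of the 16% loss change the Schoenfeld power at HR 0.62 as follows: 57.6% with no loss, 54.3% for 16% over 2.5 years, 53.5% over 2 years, 49.7% for 16% per year.

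**The case against.** The strongest reply is that the operative power claim is right. Section 4 ties 80% to explicit inputs, including HR 0.52 and a treated rate of 0.1189, and these agree with one another. On that view the 52–55% is power for an effect the calculation never used, and the only fault is a stray word. The study is also described as exploratory (SAP 3.2), no test or model changes, and the hazard ratio with its confidence interval (SAP 7.4.1) is a better guide to a null result than planning power. A 30% treated failure rate is, taken alone, higher than the cited trial's 27.45%, so there is a narrow sense in which it is cautious. Finally, the period of the 16% loss is not stated.

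Some of this stands. The 80% is correct for the rates used, and type I error is unaffected. The loss period is an inference: three years is the only reading tried that gives 72 events, and across the other readings the power at HR 0.62 runs from about 50% to 58%. Rounding 0.515 to 0.52 costs about one point of power and is minor, as is writing hazard rate for hazard ratio.

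The rest does not rescue the paragraph. Power depends on the contrast between arms, not on one arm's failure rate, and the contrast is less cautious than the precedent's. Removing the stray word makes the description accurate only by making the claim of conservatism false.

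**Conclusion.** The concern holds. Section 4 is wrong under either reading.

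- If a 30% reduction was meant, the treatment rate, hazard ratio, event count and 80% power do not belong to it. Power is 52.3% at 72 events and 54.9% at 76.7, and 139 events would be needed for 80%.
- If a 30% failure rate was meant, the calculation stands, but the effect is a 40% reduction, slightly larger than the cited trial's, and is not more conservative.

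The mismatch between a 30% reduction and 0.1189 needs only the exponential model that the plan's own rates imply. The 54.9% and the 402 subjects also rest on 16% loss over three years; the 52.3% uses the stated 72 events and does not depend on the loss. Since 0.1189 reproduces the plan's event count, the second reading is what was calculated.

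**What to change.** Correct the wording of Section 4 and carry it into the clinical study report:

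1. State that the treated arm is assumed to have a 30% three-year failure rate against 50% in control: a 40% relative reduction, rates 0.1189 and 0.2310, HR 0.515 (0.51 to two decimals).
2. Delete the claim that this is more conservative, and state that the cited design's figures imply an HR of about 0.54.
3. Add that for a 30% relative reduction (35% failure, HR 0.62) the 222-subject design has about 52–55% power, and give the period assumed for the 16% loss. Without a stated period the range is about 50–58%.

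If the sponsor's records show that a 30% reduction was intended, the 80% must not be attached to it, and the power in item 3 becomes the design's power.

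The cost is text only: no change to enrolment, the primary test or the analysis sets. The stated power becomes less favourable for the effect the text now describes.

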## 5 ANALYSIS SETS

In accordance with International Conference on Harmonization (ICH) recommendations in guidelines E3 and E9, the following analysis sets will be used for the analyses.

Detailed criteria for analysis sets will be laid out in Classification Specifications (CS) and the allocation of subjects to analysis sets will be determined prior to database hard lock.

### 5.1 Full Analysis Set (FAS)

Full Analysis Set (FAS): This population includes all subjects who are randomized. This will be the primary analysis set for efficacy analyses.

### 5.2 Per Protocol Set (PPS)

Per Protocol Set (PPS): This population includes all subjects who adhere to the protocol, i.e. all subjects who were randomized and who did not have any protocol deviations.

The criteria used to define protocol deviations adheres to the International Conference of Harmonizations (ICH) definitions of protocol deviations and are defined in section 5.2.1. Final judgments on exclusion of subjects from PPS are to be made by the Astellas study team.

The PPS will be a secondary analysis set for efficacy. Selected baseline demographic and baseline characteristics may also be summarized for the PPS.

#### 5.2.1 Reasons for Exclusion From PPS

All documented protocol deviations will be reviewed in the data review meeting prior to database lock. The following criteria listed in Table 3 may lead to subject's exclusion from PPS

**Table 3**

ICH Category	ICH Definition	ENACT Interpretation
PD [1]	Subjects who entered the study even though they did not satisfy the entry criteria	

• Subject randomized without meeting the inclusion/exclusion criteria

• Subject missed assessment(s)/procedure(s) impacting eligibility for study participation

PD [2]	Subjects who developed withdrawal criteria during the study but were not withdrawn	

• Subject developed withdrawal criteria during the study and was not withdrawn

PD [3]	Subjects who received the wrong or incorrect treatment dose	

• Subject received wrong treatment or incorrect dose, or patient taking commercial Xtandi instead of study-labeled enzalutamide, also consuming drug that should have been quarantined

PD [4]	Subjects who received excluded concomitant treatment	

• Subject took medication prohibited by the protocol

### **5.3 Safety Analysis Set (SAF)**

Safety Analysis Set (SAF): This population includes all subjects who enrolled in the study are randomized to receive study drug. Therefore, the SAF is equivalent to the FAS. This population will be used for analysis of safety data.

### **5.4 Pharmacokinetics Analysis Set (PKAS)**

Not Applicable

### **5.5 Pharmacodynamic Analysis Set (PDAS)**

Not Applicable

## **6 ANALYSIS VARIABLES**

### **6.1 Efficacy Endpoints**

#### **6.1.1 Primary Efficacy Endpoint(s)**

The primary endpoint is time to prostate cancer progression (pathological or therapeutic progression).

#### **6.1.2 Secondary Efficacy Endpoints**

The secondary endpoints are:

- Safety
  - Adverse events / treatment-emergent adverse events
  - Clinical laboratory variables (hematology, biochemistry including liver enzymes and total bilirubin)
  - Vital signs (systolic and diastolic blood pressure and pulse rate)
  - 12-lead electrocardiogram (ECG)
  - Physical examination assessments
- Incidence of negative biopsies for cancer at 1 year and 2 years
- Percent of cancer positive cores at 1 year and 2 years
- Time to PSA progression (secondary rise in serum PSA $\geq$ 25% of baseline or  $\geq$ 25% above nadir or absolute increase  $\geq$ 2ng/mL)
- Incidence of secondary rise in serum PSA $\geq$ 25% baseline or  $\geq$ 25% above nadir or absolute increase  $\geq$ 2ng/mL at 1 year and 2 years
- BFI
- SF-12 assessments
- EPIC questionnaire (urinary, sexual and hormonal domains)
- MAX-PC questionnaire

#### **6.1.3 *CCl***

### **6.2 Pharmacokinetic Variables**

Not Applicable

### **6.3 Pharmacodynamic Variables**

Not Applicable

## 6.4 Other Variables

To clearly state, the following variables are defined:

- Month = 30.4375 days. Year = 365.25 days.
- $BMI(kg/m^2) = Weight(kg) / Height(m^2)$
- Age at randomization=  $\text{floor}((\text{intck}(\text{'month'}, \text{birth date}, \text{randomization date}) - (\text{day}(\text{randomization date}) < \text{day}(\text{birth date}))) / 12)$
- Time since initial/histological diagnosis (years) =  $[(\text{date informed consent signed} - \text{date of initial/histological diagnosis}) + 1] / 365.25$ .
- Time since initial diagnosis to Randomization (years) =  $[(\text{date of Randomization} - \text{date of initial diagnosis}) + 1] / 365.25$ .
- The duration of treatment was calculated as the (last dose date – first dose date) + 1.
- Number of pills taken from one visit to the next = number of pills dispensed – number of pills returned.
- Study drug compliance at each visit is calculated as =  $[(\text{number of pills dispensed} - \text{number of pills returned}) / (4 * \text{number of days in the visit period})] * 100$ .
- Baseline results are defined as the last assessment prior to first dose of study drug, for subjects randomized to once daily enzalutamide. For subjects randomized to active surveillance, baseline is defined as the last assessment prior to or on the date of randomization.
- Treatment Emergent Adverse Events (TEAEs) are any AEs occurring on or after date of first study drug dose date (or randomization for AS) until 30 days post-treatment end date (or 1-year plus 30 days for AS).
- Treatment Phase is defined as date of first study drug dose (or randomization for AS) until either 30 days post treatment end date or (if earlier) study discontinuation date.
- 1-Year Follow-Up Phase is defined as 31 days post treatment end date until either completing 1-Year Follow-Up or (if earlier) study discontinuation date.
- Continued Follow-Up Phase is defined as the day after completing 1-Year Follow-Up phase until study discontinuation date.

Study Day is defined using the following step-wise function:

- If date of interest is on or following randomization, Study Day = Date of Interest – Randomization Date + 1;
- Else, Study Day = Date of Interest – Randomization Date.

Change from baseline is the difference between the result on a post baseline visit and baseline assessment.

Rise in serum PSA is defined as  $PSA \geq 25\% \text{ of baseline or } \geq 25\% \text{ above nadir or } \text{absolute increase} > 2\text{ng/mL}$ .

Progression-free survival is defined as the time (in months) from the date of randomization until the date of the cancer progression (pathological or therapeutic). Pathological progression is defined as increase in primary or secondary Gleason pattern by  $\geq 1$  or higher proportion of cancer positive cores ( $\geq 15\%$  increase). Therapeutic progression is defined as the earliest occurrence of primary therapy for prostate cancer (prostatectomy/radiation/focal therapy/systemic therapy).

Subjects with no cancer progression at the time of trial completion (the last study-wide subject completes a 24 month follow-up visit), discontinuation or death will be censored at the last assessment date. Subjects discontinuing therapy will not be censored until the time of study discontinuation. Additionally, subjects switching therapy during the study will be censored at the time of the initial therapy switch.

For subjects on enzalutamide, TEAEs, defined as an adverse event observed after starting administration of the study drug and until 30 days after treatment end date, are categorized as AEs. If the adverse event occurs on Day 1 and the onset check box is marked “Onset after first dose of study drug” or the onset check box is left blank, then the adverse event will be considered treatment emergent. If the adverse event occurs on Day 1 and the onset check box is marked “Onset before first dose of study drug”, then the adverse event will be categorized as medical history. If a subject experiences an event both during the pre-investigational period and during the investigational period, the event will be considered as an AE only if it has worsened in severity (i.e. it is reported with a new start date). All adverse events collected that begin within 30 days following study discontinuation will also be counted.

Percent positive cores are calculated using the number of systemically-sampled prostate regions and any targeted regions with at least one positive core divided by the total number of systematically-sampled regions and targeted regions. This implies that despite the number of samples within a given systematic or targeted region, any positive core will indicate that region as positive.

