**CCI**

#### **3.2 Study Design**

This is a multicenter, randomized, open label exploratory study, conducted in the US and Canada, evaluating the efficacy and safety of enzalutamide for extension of time to prostate cancer progression (pathological or therapeutic) in subjects with clinically localized, histologically proven prostate cancer that is categorized as low risk or intermediate risk and who are under AS. A total of 222 subjects from approximately 50 centers will be enrolled. Subjects are eligible if they were diagnosed within 6 months of screening and have been on AS. A minimum of ten cores from transrectal ultrasound-guided prostate biopsy (mpMRI targeted versus non-mpMRI targeted) are required; confirmatory biopsy before entering the study is not required and is done at the discretion of the investigator.

Low risk is defined as T1c-T2a, PSA $<$ 10, N0, M0 (or presumed N0, M0 if computerized tomography [CT]/bone scan not done due to low risk of metastases), GS  $\leq$  6, ECOG status  $\leq$  2 and estimated life expectancy  $>$  5 years. Intermediate risk is defined as T2b-T2c, PSA $<$ 20, N0, M0 (or presumed N0, M0 if CT/bone scan not done), GS  $\leq$  7 (3+4 pattern only), ECOG status  $\leq$  2 and estimated life expectancy  $>$  5 years.

Prostate cancer progression is defined as either therapeutic progression or pathological progression. Therapeutic progression is defined as the earliest occurrence of primary therapy for prostate cancer (prostatectomy / radiation / focal therapy / systemic therapy). Pathological progression is defined as increase in primary or secondary Gleason pattern by  $>$  1 or higher

proportion of cancer positive cores (>15% increase). Subjects will be stratified by low versus intermediate risk and type of biopsy performed (mpMRI targeted versus non-mpMRI targeted).

Subjects will be randomized (1:1) either to receive treatment with enzalutamide (160 mg), administered as four 40 mg capsules, by mouth, once daily or to AS during the one year study treatment period. Following the one year treatment period, all subjects will be followed for one additional year. Subjects will be followed up every 3 months for these 2 years, after which follow-up will either be every 6 months or unscheduled until the last subject finished their 2 year follow-up. Serum PSA will be measured at baseline and every 3 months during subsequent follow-up visits.

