### 7.4.1 Analysis of Primary Endpoint(s)

The primary efficacy endpoint is time to prostate cancer progression (pathological or therapeutic), and the hypothesis for analysis is:

$H_0$ : The time to progression for Enzalutamide and Active Surveillance (AS) are the

same  $H_1$ : The time to progression for Enzalutamide and AS are not the same

Median and 95% confidence intervals for time to prostate cancer progression (pathological or therapeutic) will be calculated with the Kaplan-Meier (KM) method for each treatment group. Subjects with no cancer progression at the time of trial completion, discontinuation or death will be censored at the last assessment date. Additionally, subjects switching therapy during the study will be censored at the time of the initial therapy switch, but subjects discontinuing therapy will not be censored until the time of study discontinuation. If less than 50% of subjects progress by study cut-off time, the 25th percentile and its two-sided 95% confidence interval will be reported. KM plots will be generated.

Treatment group differences between enzalutamide versus AS will be based on a Cox regression model. The resulting Hazard ratio (enzalutamide/AS) and 95% confidence interval will be included in the summary. Censoring assumptions will follow the same rules as applied for the KM estimates. Fixed effects for the model will include the treatment groups, randomization stratification factors [prostate cancer risk (low/intermediate), type of biopsy performed (mpMRI targeted/non mpMRI targeted)], age, race, and time since prostate cancer diagnosis. Additionally, a random effect of site will be included in the model.

The association between the survival time, log of time to disease progression, and survival probability, log negative log, will be investigated graphically by Cox proportional-hazards models. If the proportional hazards assumption is violated, appropriate remedial methods will be investigated and applied.

Data listings will be provided.

In addition to an overall analysis, the primary and secondary analyses will be repeated for pathological progression and therapeutic progression, individually.

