### 7.5.1 Adverse Events

All AEs will be collected and the severity of the AEs will be evaluated by the investigator based on Version 4.03 of the NCI-CTCAE criteria, updating to the latest version per sponsor decision. All AEs will be coded using the Version 23.0 of the Medical Dictionary for Regulatory Activities (MedDRA) to preferred term, high-level term and system organ class, up versioning every two years per sponsor decision.

Adverse events occurring before randomization will be recorded as medical history events. To maintain naming consistency with subjects on Active Surveillance (AS), Treatment-Emergent Adverse Events (TEAEs) for subjects on Enzalutamide will be reported as Adverse Events (AEs).

An overall summary table will be included that has the following information by treatment group and overall by analysis phase (Treatment, 1-Year Follow-Up and Continued Follow-Up):

- Number and percentage of subjects with AEs
- Number and percentage of subjects with causally drug-related AEs
- Number and percentage of subjects with serious AEs
- Number and percentage of subjects with serious drug-related AEs
- Number and percentage of subjects with AEs leading to permanent discontinuation of study drug,
- Number and percentage of subjects with drug-related AEs leading to permanent discontinuation of study drug
- Number of deaths.

Furthermore, the number of events and number (%) of subjects with AEs, drug-related AEs, serious AEs, drug-related serious AEs, AEs leading to permanent discontinuation of study drug, drug-related AEs leading to permanent discontinuation of study drug, and common AEs occurring in at least 3.5% of any treatment group will be summarized by MedDRA system organ class and preferred term by treatment group and overall. Additional summary tables will be provided for AEs by relationship to study treatment and by CTCAE maximum severity grade. For subjects with missing relationship, the most conservative (related) will be assumed for table summaries.

If a subject reports the same event multiple times, the event will only be displayed once in the summary tables at the highest grade and relationship to study drug.

Version 4.03 of the NCI-CTCAE criteria, updating to the latest version per sponsor decision, will be used to classify laboratory values by toxicity grade.

Listings of AEs, SAEs, Deaths and AEs leading to study drug discontinuation will be displayed by treatment group and site.

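### The adverse-event window ends with drug stop for enzalutamide but by the calendar for AS, so crude treatment-phase percentages compare unequal observation times whenever men stop enzalutamide early

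*SAP*

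**What the plan says.** Section 6.4 of the SAP starts the treatment-emergent window at first dose (randomization for AS) and runs it "until 30 days post-treatment end date (or 1-year plus 30 days for AS". A later paragraph of the same section restates the enzalutamide rule: events "until 30 days after treatment end date, are categorized as AEs". Both arms have the same planned period, "once daily or to AS during the one year study treatment period" (section 3.2).

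Section 6.4 also defines reporting phases. The Treatment Phase runs "until either 30 days post treatment end date or (if earlier) study discontinuation date", and the next phase follows from it: "1-Year Follow-Up Phase is defined as 31 days post treatment end date until either completing 1-Year Follow-Up or (if earlier) study discontinuation date". Neither definition gives AS a treatment end date.

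Section 7.5.1 presents the overview table "by treatment group and overall by analysis phase (Treatment, 1-Year Follow-Up and Continued Follow-Up", as numbers and percentages of subjects. It relabels enzalutamide treatment-emergent events simply as AEs, to match the AS naming. The tables by system organ class and preferred term are described without any split by phase. No rate per person-time is planned. Section 7.3.1 summarises days on therapy but links them to no adverse-event table.

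Men who stop drug stay in the study: for the primary endpoint, "subjects discontinuing therapy will not be censored until the time of study discontinuation" (section 7.4.1). Footnote 16 to Table 2 has adverse events collected from consent until the man completes the study.

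**The concern.** One arm's clock stops with the drug and the other's runs by the calendar. Leaving the study shortens observation in both arms, but stopping drug shortens it only in the enzalutamide arm. Crude percentages under one shared label then compare men watched for different lengths of time.

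An early stopper's later events are collected, but they leave the treatment-phase column. In the overview table they move to the 1-Year Follow-Up Phase. In the system organ class and preferred-term tables they may disappear, because those tables are not said to be split by phase and enzalutamide AEs are defined there as treatment-emergent ones.

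Safety is the first secondary objective listed in section 3.1, and the comparator arm receives no study drug. The treatment-phase comparison is where a reader will look for the added harm of the drug.

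**Working it through.** **Window lengths.** The SAP fixes the units: "Month = 30.4375 days. Year = 365.25 days".

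- AS: 365.25 + 30 = 395.25 days; 395.25 / 30.4375 = 12.99 months, for a man still in the study.
- Enzalutamide, stop at month m: 30.4375m + 30 days.

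| Stop at month | Window (days) | Share of AS window |
|---|---|---|
| 1 | 60.4 | 15% |
| 3 | 121.3 | 31% |
| 6 | 212.6 | 54% |
| 9 | 303.9 | 77% |

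**Effect on a crude percentage when nothing differs between arms.** The following are assumptions, not SAP figures: the same constant event hazard in both arms; AS incidence p over the full window of 10% to 80%; a fraction f of enzalutamide men stopping early, 10% to 30%; stops unrelated to adverse events, either all at month 3 or spread evenly over the year. The 16% in section 4 is loss to follow-up, so it does not supply f.

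- Hazard: λ = −ln(1 − p) / 395.25 per day.
- Stopper with window w: P = 1 − exp(−λw).
- Enzalutamide incidence: (1 − f)p + fP.

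Example with p = 30%, f = 20%, all stops at month 3: λ = 0.3567 / 395.25 = 0.000902; P = 1 − exp(−0.000902 × 121.3) = 0.104; incidence = 0.8 × 0.30 + 0.2 × 0.104 = 26.1%; ratio = 0.261 / 0.30 = 0.87.

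| p | f | Evenly spread: incidence (ratio) | All at month 3: incidence (ratio) |
|---|---|---|---|
| 10% | 10% | 9.5% (0.955) | 9.3% (0.932) |
| 10% | 30% | 8.6% (0.864) | 8.0% (0.795) |
| 30% | 20% | 27.4% (0.914) | 26.1% (0.869) |
| 30% | 30% | 26.1% (0.871) | 24.1% (0.804) |
| 80% | 10% | 77.4% (0.967) | 75.9% (0.949) |
| 80% | 30% | 72.2% (0.902) | 67.7% (0.846) |

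The ratio runs from about 0.80 to 0.97. With f = 0 it is 1.00. It is also 1.00 for any f if both arms use the same calendar window.

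**When adverse events cause the stop.** Such a man already has an event inside his window, so for the any-event percentage his probability is 1, not P. Take p = 80%, f = 20%, stops at month 3, so P = 0.390:

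- no stops event-driven: 0.64 + 0.2 × 0.390 = 71.8%;
- half event-driven: 0.64 + 0.10 + 0.1 × 0.390 = 77.9%;
- all event-driven: 0.64 + 0.20 = 84.0%, above the AS figure of 80%.

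The gap to AS closes once the event-driven share reaches (0.80 − 0.390) / (1 − 0.390) = 67%. The events removed by the short window shrink in step: 0.2 × (0.80 − 0.390) = 8.2 points with none event-driven, 0.1 × 0.410 = 4.1 points with half, and zero with all. This relief applies to the any-event count and to the event that caused the stop. It does not extend to other preferred terms or to later serious events in the same man.

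**The phase definitions.** For a stop at month 3, the follow-up phase begins after about day 121. For AS, the start has to be inferred as after about day 395. The end is not fixed for the early stopper. If the phase closes at the 24-month visit (day 730), it lasts about 730 − 121 = 609 days, against 730 − 395 = 335 for AS. If it closes one year after drug stop, it lasts 365.25 − 30 = 335 days in both arms, but over different calendar time.

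**The case against.** Drug stop plus 30 days is a conventional on-treatment window. The study is exploratory and open label, and the adverse-event tables are descriptive, with no between-arm test. That stands, and it limits the weight of the point. It does not make the two windows comparable when they are set side by side under one label.

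Four stronger readings are tempting, and the document does not support them:

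- *Every AS man is counted for a fixed 13 months.* The Treatment Phase ends at study discontinuation if that is earlier, and events are collected only while a man is in the study.
- *Later enzalutamide events are lost.* The overview table moves them to another displayed phase. Loss is possible only in tables not split by phase.
- *The more men stop for toxicity, the lower the enzalutamide any-event percentage.* The working shows the opposite tendency: event-driven stops narrow the gap and can reverse it. A shortfall of many points holds only if stopping is unrelated to adverse events and incidence is high. At 10% incidence the same model gives 0.5 to 2.0 points.
- *The bias reverses in the follow-up phase.* This depends on when that phase ends for an early stopper, which is not stated.

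One might also argue that a sentence in section 6.4 rescues the later events, since it counts those beginning within 30 days after study discontinuation. It is keyed to leaving the study, not to stopping drug, and it is silent on the interval between drug stop plus 30 days and study exit. It is a further rule to reconcile, not a remedy.

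**Conclusion.** The point holds in limited form. The windows differ by arm as written, only the enzalutamide window shrinks when drug is stopped, and the planned percentages do not adjust for it. For events that do not cause the stop, such as other preferred terms and serious events, the treatment-phase comparison is biased in enzalutamide's favour.

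The incidence ratio of about 0.80 to 0.97 under no true difference is an illustration. It rests on equal constant hazards, 10% to 30% early stoppers and stopping unrelated to adverse events, none of which the SAP supplies. Events concentrated early on drug would also shrink it. A reader might infer that enzalutamide will appear safer than it is by some fixed margin; the SAP gives no basis for such a figure.

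Apart from size, three gaps in the text need closing: AS has no treatment end date in the phase definitions (the date-imputation rules in section 7.10.1 refer to the last day of one year of surveillance, but section 6.4 does not), the completion of 1-Year Follow-Up is undefined for an early stopper, and the study-discontinuation sentence is not reconciled with the drug-stop cut-off.

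**What to change.** - For between-arm adverse-event tables, use one window in both arms: from first dose (randomization for AS) to 1 year plus 30 days, or study discontinuation if earlier, whether or not the man is still on drug.
- Start the 1-Year Follow-Up Phase at that same point in both arms, and state when it is completed.
- Keep the on-treatment-plus-30-days window as a separate table for enzalutamide only.
- Add events per 100 person-years by phase.
- Define the AS end date in section 6.4, state which window the system organ class and preferred-term tables use, and reconcile the two event definitions and the study-discontinuation sentence in section 6.4 with section 7.5.1.

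The cost is SAP wording and one more set of tables; events are already collected until study completion. The drawback is that the main table will include some off-drug events in enzalutamide men, which the retained on-treatment table separates out.
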